11	7.	Immune response including prevalence of hypersensitivity-related outcomes (e.g., asthma, atopic
12		dermatitis; higher levels of immunoglobulins (IgG, IgA and IgM) and lower antibody responses to
13		rubella, mumps, and diphtheria vaccines).
14	Neuroo	developmental outcomes (lower intelligence quotient (full scale IQ), attention-deficit and
15	hypera	ctivity disorder (ADHD).
16	For adu	ults (aged \geq 18 years), the Multi-site Study will evaluate the following main hypotheses.
17	Higher	serum levels of PFOA, PFOS, PFHxS, or other PFAS are associated with:
18	1.	Lipids (higher total cholesterol, low-density lipoprotein and triglycerides) and a higher prevalence
19		of hypercholesterolemia).
20	2.	Higher prevalence of coronary artery disease and hypertension (including hypertensive disorders
21		of pregnancy).
22	3.	Renal function (higher level of uric acid and a higher prevalence of hyperuricemia, lower
23		estimated glomerular filtration rate (eGFR)) and higher prevalence of kidney disease.
24	4.	Glycemic parameters (glucose, insulin, glycosylated hemoglobin (HbA1c), auto-antibodies (GAD-
25		65 and IA-2), C-peptide, pro-insulin) and diabetes (type 1 and 2).
26	5.	Differences in thyroid hormones (thyroid stimulating hormone (TSH), TT4, FT4, and TT3), and
27		higher prevalence of hypothyroidism/ hyperthyroidism.

1	6.	Liver function/damage biomarkers (alanine transaminase (ALT), γ -glutamyltransferase (GGT),
2		direct bilirubin, cytokeratin-18 (CK-18)) and liver disease.
3	7.	Higher prevalence of osteoarthritis and osteoporosis.
4		
5	8.	Higher prevalence of endometriosis.
6	9.	Measures of immune response and inflammation (serum levels of IgA, IgE, IgG, IgM, C - reactive
7		protein (CRP), antinuclear antibodies (ANA), inflammatory cytokines and adipokines (interleukin
8		1- β (IL-1 β), interleukin 6 (IL-6), interleukin 8 (IL-8), monocyte chemotactic protein-1 (MCP-1),
9		tumor necrosis factor α (TNF α), leptin, adiponectin, resistin, plasminogen activator inhibitor-1
10		(PAI-1).
11	10	Higher prevalence of autoimmune diseases such as ulcerative colitis, rheumatoid arthritis, lupus,
12		and multiple sclerosis.
13		
14	2.6 Int	ended Use of Study Findings
14	2.0 m	
15	Given t	hat epidemiological research on the health effects of drinking water exposures to PFAS other than
16	PFOA i	s at an early stage, the Multi-site Study should make an important contribution to the scientific

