6 For adults, **Table 2** (and **Attachment 3b**) provide the sample size calculations for several health outcomes 7 of interest assuming a type 1 (" α error") of .05 and type 2 error (" β error) of .20. In this exposure based 8 study we assume an appropriate coverage of range of exposures that will enable 9 stratification/categorization to tertiles or quartiles of exposure. Per stratum estimates of needed sample 10 size (e.g. first vs. fourth quartile) have been calculated based on different measures of association such as 11 odds ratios or detected mean difference.

12 The proposed sample size of 6,000 adults (equally of both sexes) is large enough to effectively evaluate 13 many of the health outcomes identified in the Pease Feasibility Assessment literature review. For example, for outcomes like elevated lipids levels (cholesterol) or uric acid, the range of 229 to 660 14 15 participants per stratum (i.e. quartile) or 200 to 550 per stratum, respectively, given observed differences would be needed. That would translate to overall sample size of about 800 to 2,600 participants being 16 sufficient to detect differences at the specified level of precision and power (Steenland, 2009, 2010; Fisher 17 18 2013; Shankar 2011). Similar sample sizes would also be required to compare other common health 19 outcomes such as cardiovascular disease (Shankar 2012). Larger samples sizes would be needed for liver 20 function or osteoarthritis, with a total sample in the range of 3,000 to 4,000 subjects (Uhl 2013; Gallo 21 2012; Steenland 2010).

22 For thyroid disease and thyroid function, a total sample size of 6,000 may be sufficient although probably 23 not optimal. However, NHANES studies of thyroid function and thyroid disease obtained statistically 24 significant findings with total sample sizes considerably less than 6,000 (Melzer 2010; Wen 2013). 25 NHANES studies of liver function also obtained statistically significant findings with total sample sizes 26 considerably less than 6,000 (Gleason 2015; n=4333). For biomarkers of immune function (e.g., immunoglobulins, C-reactive protein and cytokines) and fatty liver disease, there was insufficient 27 28 information to calculate sample sizes. However, a total sample size of 6,000 should be sufficient to 29 evaluate these biomarkers as we assumed similar endpoint differences of those outcomes.

For ulcerative colitis, a sample size of 6,000 might be sufficient if the effect size in the C8 study (i.e.,

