 the source via ground water, then the recipient should seek information on the extent of the
 contamination plume from the state environmental agency, EPA, and/or the industrial facility.

If the contaminated drinking water is from a municipal system, then the characteristics of the distribution system will be obtained from the water purveyor. If supply wells are used, then the recipient will request historical and current information on these wells including monthly or daily production logs and dates of operation. If a surface water source is used or if water is purchased from another purveyor, then the recipient will request information about this source.

10 The recipient will also request the results of all relevant PFAS sampling: in the surface water near the 11 drinking water intakes, in the distribution system, in the supply wells and nearby monitoring wells, in 12 purchased water from other water purveyors, and in the private wells in the study area.

13

14 **3.10 Statistical Analyses**

15 ATSDR staff will perform statistical analyses with the participation of the recipients using SAS, R and STATA 16 on the combined multi-site study dataset. ATSDR staff may also use SPSS for data management. ATSDR 17 staff will calculate descriptive statistics (including means, geometric means, medians, standard deviations, 18 and percentiles) to identify the presence and distribution of PFAS and effect biomarker analytes. Statistical 19 methods will include multiple linear regression of continuous (untransformed and natural log transformed) effect biomarkers on continuous (untransformed and natural log transformed) PFAS serum 20 21 levels and categorized PFAS serum levels, and logistic regression of categorized effect biomarkers (e.g., 22 hypercholesterolemia) or disease prevalence on continuous (untransformed and natural log transformed) 23 and categorical PFAS serum levels. ATSDR staff will use restricted cubic spline methods (or generalized 24 additive models using cubic regression splines) for linear and logistic regression to obtain flexible, 25 smoothed exposure-response curves. To identify risk factors that may act as confounders for a particular health outcome, the analysis will implement a "10% change in the estimate" rule (Maldonado 1993). 26

Primary analyses will focus on estimated cumulative PFAS serum levels. Supplemental analyses will
evaluate PFAS serum levels in the blood specimens obtained in the study as well as estimated maximum

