For PFOS, there was a -5.9% difference in the natural log IGF-1 among boys (per interquartile range of the natural log of PFOS). This would require considerably smaller sample sizes for IGF-1 than those for PFHxS.

Thyroid function – Children/Adolescents

Taiwan study of children. (Lin 2013)

a. For males aged 12-19, there was a mean difference in the log TSH of -.50 mIU/L for PFOA levels in the 90th percentile (>9.71 ng/ml) compared to the reference level of PFOA exposure. The standard error for the reference group was 0.26 with N=32 in this group; and the standard error for the 90th percentile group was 0.33

with N=6. The standard deviations for the reference and 90th percentile groups were therefore 1.47 and 0.81, respectively.

Assuming a 95% CI and 80% power, the sample size = 89/group; for a ratio of 2, the sample sizes = 158 and 79.

b. For females aged 12-19, there was a mean difference in the log TSH of -.35 mIU/L for PFOA levels in the 90th percentile (>9.71 ng/ml) compared to the reference level of PFOA exposure. The standard error for the reference group was 0.18 with N=71 and the standard error for the 90th percentile group was 0.24 with N=14. The standard deviations for the reference and 90th percentile groups were therefore 1.52 and 0.90, respectively.

Assuming a 95% CI and 80% power, the sample size = 200/group; for a ratio of 2, the sample sizes = 348 and 174.

Additional notes:

Sample sizes for the categorical outcomes in Table 1 were based on the following prevalence in children (also listed in Appendix C Table 1):

Hypercholesterolemia: 34.2% Hyperuricemia: 16% Thyroid disease: 0.6% ADHD 12.4% reported only; 5.1% reported with additional reporting on medications used for ADHD Asthma: 11% Rhinitis: 25.6% Atopic dermatitis: 10.7% Hypertension: 23.4% Obesity: 17%

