Assuming a 95% CI and 95% power, the sample size = 68/group.

a. TSH

In Ji 2012, the sample size was 633, \geq 12 years of age and the median TSH level was 1.37 µIU/mL with an IQR of 0.90, 2.01. The standard deviation was estimated as the IQR range divided by 1.35: (2.01 - .90)/1.35 = 0.82. This standard deviation was assumed for each group. For TSH, the linear regression coefficients for PFOS and PFHxS were 0.062 and 0.013, respectively. Using a PFOS level of 15 ng/mL and a PFHxS level of 9 ng/mL, the mean difference for PFOS and PFHxS are 0.93 and 0.12, respectively.

Assuming a 95% CI and 80% power, the sample size = 13/group for PFOS

Assuming a 95% CI and 80% power, the sample size = 733/group for PFHxS

b. TT₄ (total thyroxine)

In Ji 2012, the sample size was 633, \geq 12 years of age and the median TT₄ level was 7.4 µg/dL and the IQR was 6.7, 8.1. The standard deviation was estimated: (8.1 – 6.7)/1.35 = 1.04. This standard deviation was assumed for each group. For TT₄, the linear regression coefficients for PFOS and PFHxS were -0.021 and - 0.007, respectively. Using a PFOS level of 15 ng/mL and a PFHxS level of 9 ng/mL, the mean difference for PFOS and PFHxS are -0.32 and -0.06, respectively.

Assuming a 95% CI and 80% power, the sample size = 166/group for PFOS

Assuming a 95% CI and 80% power, the sample size = 4,716/group for PFHxS

Sample sizes for the categorical outcomes in Table 2 were based on the following prevalences in adults:

Hypercholesterolemia: 15% Hyperuricemia: 24% Thyroid disease: 6.5% (reported and confirmed by medical records); 11.5% (reported only) Elevated ALT: 11.2% Elevated GGT: 14% Elevated bilirubin: 1.1% Osteoporosis: 5% Osteoarthritis: 7.6% Cardiovascular disease: 13% Ulcerative colitis: 0.5% Rheumatoid arthritis: 1.2%

Health related Endpoints Not shown in Table 2:

Chronic kidney disease: 1.4% Liver disease: 2% Hypertension: 37% Pregnancy-induced hypertension: 8.5% Endometriosis: 7% Lupus: 0.2% Multiple sclerosis: 0.32% Kidney cancer: 0.3%

Multi-site Study – Eligibility Screening Script

Multi-site Study Eligibility Screening Script Flesch-Kincaid Readability Score – 5.8

> Form Approved OMB No. 0923-XXXX Exp. Date xx/xx/201x

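### Section 3.10 applies logistic regression on PFAS categories to every disease with no sparse-outcome rule, yet about 12 lupus and 19 multiple sclerosis cases are expected; a penalised fit is the better choice for those categorical models

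*Protocol*

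**What the plan says.** Protocol section 3.10 lists the methods for binary outcomes as "and logistic regression of categorized effect biomarkers (e.g"., "hypercholesterolemia) or disease prevalence on continuous (untransformed and natural log transformed") and on categorical PFAS levels. It names no estimator, gives no rule for outcomes with few cases, and selects confounders by a 10% change-in-estimate rule. It adds that findings will be judged by the size of the effect estimates, with confidence intervals showing their precision.

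The rare diseases are named among the adult hypotheses in section 2.5.2 (number 10): "Higher prevalence of autoimmune diseases such as ulcerative colitis, rheumatoid arthritis, lupus" and multiple sclerosis. Attachment 3b gives their prevalences in per cent: "Lupus: 0.2% Multiple sclerosis: 0.32" and "Ulcerative colitis: 0.5". Section 3.3.2 sets the adult sample at 6,000. Exposure categories are tertiles or quartiles, with quartiles preferred in section 3.3.1 and Attachment 3b.

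**The concern.** A quartile model compares each upper quartile with the reference quartile. If either the top or the reference quartile has no case, the maximum-likelihood odds ratio for that contrast is zero or infinite and has no usable Wald interval. With 12 cases spread over four quartiles this is not a remote event. When the estimate is finite but rests on two or three cases, the Wald standard error is so large that the test almost never rejects.

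This bears on the protocol's own basis for interpretation, which is effect size and confidence interval rather than significance alone. A 10% change-in-estimate rule also cannot be applied to an odds ratio that is not finite. If failed fits are simply left out, the remaining estimates are a selected set.

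**Working it through.** **Inputs from the protocol.** 6,000 adults (3.3.2); prevalences 0.2%, 0.32% and 0.5% (Attachment 3b); two-sided alpha 0.05 and 80% power (3.3, Attachment 3); odds ratio 3.05 for ulcerative colitis (Table 2); quartiles, so 6,000 / 4 = 1,500 each.

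**The plan's own figure.** Table 2 gives 1,480 per stratum for ulcerative colitis. With p1 = 0.005, p2 = 3.05 × 0.005 / (1 + 2.05 × 0.005) = 0.0151, and the pooled two-proportion formula n = [z(1-α/2)·√(2p̄q̄) + z(1-β)·√(p1q1 + p2q2)]² / (p2 - p1)², I get 1,531. That is 3.4% higher (1,497 if 3.05 is read as a prevalence ratio). The same formula matches several other Table 2 rows within 2, so the gap is local to this row and does not affect this point.

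**Expected cases.** 6,000 × 0.002 = 12; 6,000 × 0.0032 = 19.2; 6,000 × 0.005 = 30.

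**Chance of no finite odds ratio, by hand.** Let the log odds ratio rise evenly over quartiles, so case shares are proportional to OR^0, OR^(1/3), OR^(2/3) and OR^1. Treat quartile counts as Poisson. The top-versus-reference estimate fails if either quartile is empty: P = 1 - (1 - e^-r)(1 - e^-t), where r and t are the expected cases in the reference and top quartiles.

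- 12 cases, OR 1: r = t = 3; P = 1 - (1 - 0.0498)² = 9.7%.
- 12 cases, OR 3.05: weights 1 + 1.450 + 2.103 + 3.05 = 7.603; r = 12 / 7.603 = 1.578, t = 4.814; P = 21.3%.
- 19.2 cases: OR 1, r = t = 4.8, P = 1.6%; OR 3.05, r = 2.525, t = 7.702, P = 8.1%.
- 30 cases: OR 1, r = t = 7.5, P = 0.1%; OR 3.05, r = 3.946, t = 12.034, P = 1.9%.

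No site term or covariate enters this calculation.

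**Simulation.** 2,500 data sets per scenario; assumed six equal sites, sex, three age bands and exposure quartiles; maximum likelihood (ML) with a Wald or likelihood-ratio test (LRT), against Firth with a penalised likelihood-ratio test. Monte Carlo error at a 5% rate is √(0.05 × 0.95 / 2,500) = 0.4 points.

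| Top v reference quartile | 12 cases | 19 cases | 30 cases |
|---|---|---|---|
| ML not finite, OR 1 to 3.05 | 10-22% | 2-7% | 0.1-2% |
| Type I error, ML Wald | 0.4% | 1.9% | 4.0% |
| Type I error, ML LRT | 9.6% | 8.6% | 7.1% |
| Type I error, Firth | 3.1% | 4.5% | 5.4% |
| Power OR 2, ML Wald v Firth | 2.1% v 9.3% | 8.8% v 15.5% | 20.4% v 24.1% |
| Power OR 3.05, ML Wald v Firth | 4.6% v 18.8% | 20.3% v 32.4% | 44.5% v 50.3% |

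Firth gave finite estimates in every data set. The ML likelihood-ratio test has more power (31%, 41% and 54% at OR 3.05), but its type I error is inflated.

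**Without site terms.** A run of 1,500 data sets per scenario with quartiles, sex and four age groups gave non-finite contrasts in 9%, 14% and 23% (12 cases; OR 1, 2, 3.05) and 2%, 4% and 9% (19 cases). At 12 cases and a true OR of 3.05, the finite ML estimates had a geometric mean of 2.49; Firth over all data sets gave 2.94.

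**Continuous exposure.** The ML exposure coefficient was finite in every run. Power at OR 3.05 was 22.5%, 35.4% and 52.0% with ML Wald and 23.2%, 35.7% and 52.2% with Firth, so there is no gain. Firth with a Wald test rejected a true null in 9.5% of runs at 12 cases, which is why the interval type has to be stated.

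**The case against.** The strongest reply is that section 3.10 does not say maximum likelihood. Firth regression is logistic regression, the wording is not exclusive, and the estimator may be set in an SAP that is not shown. That stands in part: standard ML is inferred as the default meaning of an unqualified term. The protocol nevertheless fixes one method for diseases with a dozen cases and for those with thousands, and makes the categorical model part of it.

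Second, the protocol already concedes the problem. It calls 6,000 adults too few for rare diseases and inadequate for ulcerative colitis at odds ratios below 2.75. That stands for power. It does not address estimates that do not exist, and the analyses remain planned.

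Third, the same sentence already plans continuous exposure, which behaves well. That stands too, and limits the point to the categorical models.

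Stronger readings are tempting but not supported:

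- A reader might infer that most such fits break down. With six site terms, some coefficient is non-finite in 64-68% of data sets at 12 cases, but mostly because a site has no case. The protocol specifies no site terms, and an empty site does not make the exposure odds ratio infinite.
- A reader might extend the point to child thyroid disease, where "Thyroid disease: 0.6"% of 2,000 is 12. The child hypothesis concerns hypo- and hyperthyroidism, which section 3.7.1 derives from measured hormones and includes subclinical disease, so 12 is not shown to be its count.
- A reader might infer that Firth restores power. It does not; no scenario exceeded about 52%.

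**Conclusion.** The point holds for categorical-exposure models of outcomes with about 20 or fewer cases: lupus and multiple sclerosis on the protocol's own prevalences. There, ML leaves the main contrast undefined in roughly 10-22% (12 cases) or 2-9% (19 cases) of data sets, and its Wald test runs at about 0-2% instead of 5%. At an odds ratio of 3.05, Firth recovers about 14 points of power at 12 cases and 12 at 19. At 30 cases (ulcerative colitis) the contrast is finite in about 98% or more of data sets and the gain is about 6 points, so a change there is optional. Rheumatoid arthritis, at 6,000 × 1.2% = 72 cases, is outside the range examined.

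Assumptions: quartiles; a log-linear effect across them; exposure unrelated to site; and the Attachment 3b prevalences applying to all 6,000 adults. If 0.2% were instead the reference-quartile prevalence, as the sample-size formula uses it, that quartile would expect 1,500 × 0.002 = 3 cases, and the failure rate at 12 cases would be about 5-10% (e^-3 = 5.0% at high odds ratios, 9.7% at OR 1). Tertiles would also lower it. This is an inexpensive improvement to the plan and does not show that the study's main analyses are unsound.

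**What to change.** Add to section 3.10: for any disease with about 20 or fewer observed cases in total, counted before looking at the split by exposure,

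- fit categorical-exposure models by Firth penalised logistic regression and report penalised profile-likelihood intervals and tests, not Wald;
- take the continuous or trend exposure term as the lead estimate, with the categorical contrasts as supporting information;
- use a short covariate list fixed in advance in place of the 10% change-in-estimate rule;
- label the results exploratory.

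The cost is one model option in software the protocol already names (SAS, R), with no new data. Estimates are slightly shrunk. The change does not supply the missing cases, so the protocol's statement that the sample is too small for rare diseases should stay.
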